5.8.3.3 QT Prolongation

Guidelines for dose modification and stopping criteria due to QTc-prolongation are provided in [Table 8](#).

Table 8 Withholding and Stopping Criteria for QTc-Prolongation

QTc-Prolongation ^a	Action and Dose Modification

 • QTc ≥501 msec 	
 • Interrupt study treatment until QTc prolongation resolves to grade 1 or baseline • Test serum potassium, calcium, phosphorus and magnesium. If abnormal correct per routine clinical practice to within normal limits. • Review concomitant medication usage for agents that prolong QTc. • If event resolves, restart study treatment at current dose level^b • If event does not resolve, permanently discontinue study treatments. Consider evaluation with cardiologist. • If event recurs, permanently discontinue study treatments. Consider evaluation with cardiologist.

Abbreviations: msec = milliseconds; QTc = QT interval on electrocardiogram corrected

- Based on average QTc value of triplicate ECGs. For example, if an ECG demonstrates a prolonged QT interval, obtain two or more ECGs over a brief period, and then use the averaged QTc values of the three ECGs to determine if study treatments should be interrupted or discontinued.
- If the QTc prolongation resolves to grade 1 or baseline, the subject may resume study treatment if the investigator and Novartis Medical Lead agree that the subject will benefit from further treatment.

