7.3.11 Other Safety Outcomes

Laboratory Assessments

All protocol-required laboratory assessments must be performed by the central laboratories. Laboratory assessments must be conducted in accordance with the Central Laboratory Manual and Protocol Time and Events Schedule ([Table 20](#)).

If additional non-protocol specified laboratory assessments are performed at the institution's local laboratory and they result in a change in patient management (for example SAE or AE or dose modification) the results must be recorded in the subject's CRF. Refer to the SPM for appropriate processing and handling of sample to avoid duplicate and/or additional blood draws.

Laboratory requisition forms must be completed and samples must be clearly labelled with the subject number, protocol number, site/center number, and visit date. Details for the preparation and shipment of samples, and a list of reference ranges for all safety parameters will be provided to the site by the central laboratory in a separate instruction manual.

Clinical chemistry and hematology parameters to be tested are listed in [Table 22](#). Female subjects will have a serum pregnancy test at Screening; urine pregnancy testing may be done during study treatment, if necessary.

Table 22 Clinical Chemistry and Hematology Parameters

Clinical Chemistry Parameters
Albumin Alkaline Phosphatase Alanine Transaminase (ALT) or Serum Glutamic Pyruvic Transaminase (SGPT) Aspartate Aminotransferase (AST) or Serum Glutamic Oxaloacetic Transaminase (SGOT) Gamma-Glutamyl Transpeptidase (GGT) Bicarbonate Blood Urea Nitrogen (BUN) or urea Calcium Chloride Creatinine ^c Glucose (random) Lactate Dehydrogenase (LDH) Magnesium Phosphate Potassium Sodium Total Bilirubin ^b Total Protein
Hematology Parameters
White Blood Cell (WBC) Count Hemoglobin Hemoglobin A1C Hematocrit International Normalized Ratio (INR; at Screening only) ^a Platelet Count Prothrombin Time (PT; at Screening only) ^a Partial Thromboplastin Time (PTT; at Screening only) ^a Automated WBC Differential (expressed as GI/L): Basophils Eosinophils Lymphocytes Monocytes Neutrophils
Other tests
Amylase and lipase [monitor via local laboratory where appropriate to evaluate certain AEs (i.e., abdominal pain, pancreatitis, etc.)]
serum β -hCG (human chorionic gonadotrophin)

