9.3.5.2.3 Clinical Laboratory Evaluations

Hematology and clinical chemistry data will be summarized at each scheduled assessment according to NCI CTCAE grade (v4.0). The proportion of values lying outside the reference range will also be presented for laboratory tests which are not graded because there are no associated NCI CTCAE criteria (v4.0). Summaries by visit will include data from scheduled assessments only and all data will be reported according to the nominal visit for which it was recorded (i.e. no visit windows will be applied). Unscheduled data will be included in 'worse case post baseline' summaries which will capture a worst case across all scheduled and unscheduled visits after the first dose of study treatment. Further details will be provided in the SAP.

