2.8.3 Laboratory data

The assessment of laboratory toxicities will examine the following laboratory tests:

Hematology: Hemoglobin (HGB), White Blood Cell (WBC) count, Total Neutrophils, Lymphocyte, Monocyte, Basophil and Eosinophil counts, and Platelet count. Basophils, Eosinophils and Monocytes are not gradable by CTCAE v4.0.

Clinical Chemistry: Sodium, Potassium, Calcium, Glucose, Blood Urea Nitrogen (BUN), Creatinine, Estimated Creatinine Clearance, Albumin, Lactate Dehydrogenase (LDH), and phosphate. BUN, LDH and Estimated Creatinine Clearance are not gradable by CTCAE v4.0. For Sodium, Potassium, Calcium, Phosphate, Lymphocyte and Glucose two bi-directional parameters (hyper and hypo), the tests will be graded by CTCAE v4.0 in both directions.

Liver Function Tests: Aspartate amino transferase (AST), Alanine amino transferase (ALT), Alkaline phosphatase, Total bilirubin (total) and Direct bilirubin. All these tests are gradable by CTCAE v4.0.

Coagulation Tests: Prothrombin time (PT) or International Normalized Ratio (INR), and partial thromboplastin time (PTT). These tests are collected only at baseline. Therefore these tests will not appear in any summaries of changes from baseline.

Summaries of worst case grade increase from baseline grade will be provided for all the lab tests that are gradable by CTCAE v4.0. These summaries will display the number and percentage of subjects with a maximum on-therapy grade increasing from their baseline grade. Any increase in grade from baseline will be summarized along with any increase to a maximum grade of 3 and any increase to a maximum grade of 4. Missing baseline grade will be assumed as grade 0. In addition, the summary will include grade increase from baseline by scheduled visits. For laboratory tests that are graded for both low and high values, summaries will be done separately and labeled by direction, e.g., sodium will be summarized as hyponatremia and hypernatremia.

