3.2 Power for analysis of key secondary variables

Not applicable.

4 Change to protocol specified analyses

Replace All Treated Subjects (ATS) to Full Analysis Set (FAS).

Mainland Chinese patients data from 01-Jul-2019 onwards are not included due to local regulations in China (lack of HGRAC approval).

5 Appendix

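### The SAP laboratory panel leaves out seven tests that the protocol collects and commits to summarising, and does not declare the reduction

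*SAP*

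**What the plan says.** Protocol 7.3.11, Table 22, sets the central laboratory panel. Its chemistry list includes "Gamma-Glutamyl Transpeptidase (GGT) Bicarbonate Blood Urea Nitrogen (BUN) or urea Calcium Chloride" and, further down, "Lactate Dehydrogenase (LDH) Magnesium Phosphate Potassium Sodium Total Bilirubin", followed by total protein. Its haematology list includes HbA1c and haematocrit. Only INR, PT and PTT are marked as screening tests. Table 20 schedules chemistry and haematology at screening, Day 1, every 4 weeks and treatment discontinuation.

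Protocol 9.3.5.2.3 states the analysis: "Hematology and clinical chemistry data will be summarized at each scheduled assessment according to NCI CTCAE grade (v4.0". For tests without CTCAE criteria it promises the proportion of values outside the reference range. It exempts no test and leaves further detail to the SAP. Protocol 9.3.5 says that deviations from the planned analysis are to be documented in the SAP and the final report.

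SAP 2.8.3 begins "The assessment of laboratory toxicities will examine the following laboratory tests" and gives four lists: haematology, chemistry, liver function and coagulation. After sodium, potassium, calcium and glucose, the chemistry list ends "Blood Urea Nitrogen (BUN), Creatinine, Estimated Creatinine Clearance, Albumin, Lactate Dehydrogenase (LDH), and phosphate". SAP Section 4 records two changes from the protocol: the renaming of the analysis set ("Replace All Treated Subjects (ATS) to Full Analysis Set (FAS") and the data cut-off for Mainland Chinese patients.

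**The concern.** Laboratory values are a named safety endpoint in both documents. A programmer who builds the tables from the SAP's named lists would produce no grade-increase, shift or normal-range table for the seven tests. The protocol promises such summaries, and nothing in the SAP says that they were dropped on purpose.

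Magnesium shows the problem best. Table 8 of the protocol, on QTc prolongation, says "Test serum potassium, calcium, phosphorus and magnesium", and exclusion criterion 12 gives hypomagnesaemia as an example beside low potassium and low calcium. The SAP tabulates potassium, calcium and phosphate but not magnesium.

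What is at stake is the aggregate picture: how many subjects moved to a worse grade or out of range on a test when the change was not reported as an adverse event.

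**Working it through.** The documents give no figure to reproduce. The check is a set comparison of Table 22 with the lists in SAP 2.8.3.

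**Inputs**

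- Table 22, chemistry: 18 tests.
- Table 22, haematology and coagulation: 13 tests, of which 3 (INR, PT, PTT) are done at screening only.
- SAP 2.8.3: 26 named tests, counting PT and INR separately (8 haematology, 10 chemistry, 5 liver, 3 coagulation).

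**Comparison**

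| Group in Table 22 | Tests | Named in SAP 2.8.3 | Not named |
|---|---|---|---|
| Chemistry | 18 | 13 | 5: magnesium, GGT, bicarbonate, chloride, total protein |
| Haematology, repeated | 10 | 8 | 2: HbA1c, haematocrit |
| Coagulation, screening only | 3 | 3 | 0 |
| Total | 31 | 24 | 7 |

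The SAP also names two items that are not in Table 22's parameter lists: estimated creatinine clearance and direct bilirubin. This reconciles the counts, since 24 + 2 = 26.

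**Size**

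- Whole panel: 7/31 = 23%.
- Tests repeated after baseline: 31 − 3 = 28, and 7/28 = 25%.
- Chemistry alone: 5/18 = 28%.

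**Is the SAP list exhaustive?** Three features suggest that it is. It carries no wording that would mark it as a set of examples. Its notes on which tests cannot be graded, and on which are graded in both directions, cover only named tests, so none of the seven is classified. It is also the only place where the SAP specifies which tests are analysed.

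Two features point the other way. The same section promises grade-increase summaries for every test gradable under CTCAE v4.0. It also promises worst-grade and shift tables for haematology and biochemistry by parameter, without tying either promise to the list.

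**Is the omission explained elsewhere?** The SAP usually says when it leaves something out. Hepatitis tests are to be listed only (2.8.3), coagulation is baseline only (2.8.3), and demographics (2.3), prior anti-cancer therapy (2.4.2.1) and pharmacokinetics (2.9) were reported with the primary analysis. No such statement covers the seven tests.

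**The case against.** The strongest reply is that little is lost. SAP 2.8.3 keeps listings of all laboratory data, with grades and range classification, and a separate listing of grade 3 or 4 toxicities. Protocol 7.3.3 requires clinically significant results, and any result that led to an intervention, to be recorded as adverse events, which then enter the adverse event tables of SAP 2.8.1. This stands. A reader might infer that abnormalities in these tests vanish from the safety tables, or can be seen only patient by patient in listings. The documents do not support either inference.

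A reader might also argue that GGT is needed for the protocol's hepatobiliary monitoring. The documents do not support this either. The stopping criteria in protocol 5.9.1 use ALT, bilirubin and INR; the repeated liver chemistries are ALT, AST, alkaline phosphatase and bilirubin; and GGT is not in the follow-up list of 5.9.1.1. The case for GGT rests only on Table 22 and 9.3.5.2.3.

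For magnesium, Table 8 and exclusion 12 govern individual patients and do not themselves call for a population table. They show that the protocol treats magnesium as relevant. The commitment to summarise it comes from 9.3.5.2.3.

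Finally, this is the close-out SAP, and the seven tests may have been tabulated for the primary report. The documents do not show this, and SAP 2.8.3 does not rely on it. It may limit the impact but does not resolve the discrepancy.

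**Conclusion.** The discrepancy is real and minor. Seven tests that the protocol collects repeatedly and commits to summarising are missing from the SAP's named panel, and SAP Section 4 does not say so. If the named list governs, they leave the aggregate laboratory summary tables. They remain in the listings, including the grade 3 or 4 listing, and in the adverse event tables when reported as adverse events. What goes uncounted is grade or range change not reported as an adverse event.

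The conclusion assumes that the named list defines which tests are tabulated. If the broader sentences govern instead, some or all of the seven may be tabulated, and the defect is then an unclear specification. Either way the text needs correcting. The count of tests (7 of 28 repeated tests) measures how much of the panel is missing, not how much safety information is lost; haemoglobin and glucose, for example, are still summarised where haematocrit and HbA1c are not.

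**What to change.** Add magnesium, GGT, bicarbonate, chloride, total protein, HbA1c and haematocrit to the lists in SAP 2.8.3. Send each to the grade tables if it is gradable under CTCAE v4.0, and otherwise to the reference-range tables; the documents do not say which of the seven are gradable, so the sponsor should settle this against the CTCAE text. State that the resulting list is exhaustive. If the sponsor prefers to leave some tests out, HbA1c or haematocrit for instance, record that with a reason in SAP Section 4.

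The cost is a few extra table rows, or a sentence in Section 4. The protocol already requires these tests, so no new data collection is needed.

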2.8.4 Other safety data

2.8.4.1 ECG and cardiac imaging data

A summary of the number and percentage of subjects who had normal and abnormal (clinically significant and not clinically significant) ECG findings will be displayed by scheduled visits.

The QT and QTcB values based on Bazett formula will be rounded to the integer and the values will be categorized into the following ranges: Grade 0 (≤ 450), Grade 1 (> 450 and ≤ 480), Grade 2 (> 480 and ≤ 500), and Grade 3 (> 500). Summaries of grade increase will be provided. These summaries will display the number and percentage of subjects with any grade increase, increase to grade 2 and increase to grade 3 at each scheduled in the worst case post baseline only.

The changes in QT and QTcB values will be categorized into the clinical concern ranges which are specific to changes in QT and QTcB: (> 30 and ≤ 60) and (> 60) msec. A summary of change in QTcB value will display the number and percentage of subjects with a change within each range at each scheduled assessment time and in the worst case post baseline. Worst case post baseline will include both scheduled and unscheduled visits. Subjects with missing baseline values will be excluded from this summary.

The summaries for the QTcB will use the collected value based on Bazett formula. In addition, ECG interval values will be also be summarized.

Listings of abnormal ECG findings and a listing of ECG values will be provided.

LVEF Absolute change from baseline in LVEF will be summarized at each scheduled assessment time and in the worst case post baseline. Only the post baseline assessments that used the same method (ECHO or MUGA) as the baseline assessments will be used to derive the change from baseline. The change from baseline will be categorized as follows:

- Any increase
- No change
- Any decrease
 - > 0 - < 10 Decrease
 - 10 - 19 Decrease
 - ≥ 20 Decrease
- ≥ 10 decrease and \geq LLN
- ≥ 10 decrease and $<$ LLN
- ≥ 20 decrease and \geq LLN
- ≥ 20 decrease and $<$ LLN

LVEF results will also be listed with subject level details including absolute change from baseline.

Note: If there is any change in the methodology used throughout the study compared to baseline, the post-baseline values for which the methodology differs from baseline will be discarded in the tables presenting comparisons to baseline.

Data handling

In case the study requires ECG replicates at any assessment, the average of the ECG parameters at that assessment should be used in the analyses.

Data analysis

12-lead ECGs including QT, QTcB, and RR intervals will be obtained local for each subject during the study. ECG data will be read and interpreted locally

The number and percentage of subjects with notable ECG values will be presented.

- QT, QTcF, or QTcB
 - New value of > 450 and ≤ 480 ms
 - New value of > 480 and ≤ 500 ms
 - New value of > 500 ms
 - Increase from Baseline of > 30 ms to ≤ 60 ms
 - Increase from Baseline of > 60 ms
- RR
 - value < 600 ms
 - value ≥ 600 ms

A listing of all ECG assessments will be produced and notable values will be flagged. A separate listing of only the subjects with notable ECG values may also be produced. In the listing, the assessments collected during the post-treatment period will be flagged.

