12.3 Appendix 3: QT interval on electrocardiogram corrected using the Bazett's formula (QTcB)

The correction method must be collected for ECG machines with a QT correction method programmed by the manufacturer. For purposes of data analysis, QTcB will be used.

If the ECG machine does not calculate QTc using Bazett's formula, QTcB should be calculated manually and entered on the eCRF.

Bazett's formula used to correct QT interval for heart rate is:

$$QTcB = \frac{QT}{\sqrt{RR}}$$

where QTcB is the QT interval corrected for heart rate, RR is the interval from the onset of one QRS complex to the onset of the next QRS complex, *measured in seconds*, often derived from the heart rate (HR) as 60/HR, and QT is the QT interval *measured in milliseconds*.

References

Bazett HC. An analysis of the time-relations of electrocardiograms. Heart 1920; 7: 353-370.

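### SAP 2.8.4.1 grades uncorrected QT on the same millisecond bands as QTcB, and names QTcF once without saying how it is obtained

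*SAP*

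**What the plan says.** SAP 2.8.4.1 describes the QT analysis in two places.

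- **Grade and change summaries.** The section states that "The QT and QTcB values based on Bazett formula will be rounded to the integer and the values will be categorized" into Grades 0 to 3, cut at 450, 480 and 500 ms. Summaries of grade increase follow. For change from baseline it defines bands of >30 to ≤60 ms and >60 ms, calling them "clinical concern ranges which are specific to changes in QT and QTcB". The change summary it then specifies is for QTcB only. On the source of the corrected value: "The summaries for the QTcB will use the collected value based on Bazett formula".
- **Notable values (Data analysis paragraph).** Counts and percentages are planned for "QT, QTcF, or QTcB", using the same 450/480/500 ms limits and the same change bands. RR is split at 600 ms.

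On what is recorded, the SAP says "12-lead ECGs including QT, QTcB, and RR intervals will be obtained local for each subject during the study". Protocol 7.3.15 lists heart rate, PR, QRS, QT, RR and QTcB. Neither list contains QTcF. Protocol Appendix 3 gives the Bazett formula and adds: "For purposes of data analysis, QTcB will be used". Fridericia's correction is in the protocol's abbreviation list, but no formula is given in either document. SAP section 4, which lists changes to the protocol's analyses, does not mention QTcF.

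**The concern.** An uncorrected interval and a rate-corrected interval are different quantities. QT shortens as the heart speeds up, and a correction exists to remove that dependence. If both are read against one set of limits, at least one table partly reports heart rate. Elsewhere the protocol attaches its QT limits to the corrected value: exclusion criterion 11b uses a Bazett QTc of 480 ms, and Table 8 uses a QTc of 501 ms. Neither document gives a reason for applying the SAP's bands to uncorrected QT.

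Two things are at stake. First, the safety report can show contradictory grades for the same tracing, with nothing in the plan to say which is to be believed. Second, the study has a single arm, so no control group shows how much of a shift is due to rate. A second correction is the usual check on Bazett. The SAP gestures at one but leaves the programmer to guess whether QTcF is collected or derived, and whether the word joining the three measures means three separate tables, a choice of one, or a composite of any of them.

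**Working it through.** The plan states no figure to reproduce, so the check applies its bands to its own variables.

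**Inputs.** Bands from SAP 2.8.4.1, after rounding to the integer: Grade 0 up to 450 ms, Grade 1 above 450 to 480, Grade 2 above 480 to 500, Grade 3 above 500. QTcB = QT/√RR, with RR = 60/HR in seconds, from protocol Appendix 3. QTcF = QT/RR^(1/3) is the standard Fridericia form and is not written out in the documents. The QT and heart-rate pairs are illustrative.

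**Step 1: the two graded quantities disagree, using the protocol's formula alone.**

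- 100 bpm, QT 390 ms: RR = 0.600 s and QTcB = 390/√0.600 = 503 ms. Grade 0 as QT, Grade 3 as QTcB.
- 50 bpm, QT 455 ms: RR = 1.200 s and QTcB = 455/√1.200 = 415 ms. Grade 1 as QT, Grade 0 as QTcB.
- A QTcB of 510 ms (Grade 3) goes with a QT of 450 ms or less (Grade 0) once HR ≥ 60 × (510/450)² = 77 bpm.

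The third line shows that the disagreement does not need an extreme rate. For comparison, QTcF is 462 ms (Grade 1) for the first tracing and 428 ms (Grade 0) for the second.

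**Step 2: rate alone, with QTcF held fixed.** Holding QTcF constant is an assumption that stands in for unchanged repolarisation.

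| QTcF held at | HR (bpm) | QT (ms), grade | QTcB (ms), grade |
|---|---|---|---|
| 440 (Grade 0) | 50 | 468, Grade 1 | 427, Grade 0 |
| 440 | 60 | 440, Grade 0 | 440, Grade 0 |
| 440 | 100 | 371, Grade 0 | 479, Grade 1 |
| 460 (Grade 1) | 60 | 460, Grade 1 | 460, Grade 1 |
| 460 | 100 | 388, Grade 0 | 501, Grade 3 |
| 505 (Grade 3) | 60 | 505, Grade 3 | 505, Grade 3 |
| 505 | 80 | 459, Grade 1 | 530, Grade 3 |
| 505 | 100 | 426, Grade 0 | 550, Grade 3 |

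**Step 3: change from baseline.** With QTcF fixed at 400 to 440 ms and the rate rising from 60 to 100 bpm, QTcB rises by 35.5 to 39.1 ms, which falls in the >30 to ≤60 ms band. Uncorrected QT falls by 63 to 69 ms. The two measures move in opposite directions with no change in QTcF.

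**Step 4: the notable-value list.** If it is programmed as any of the three measures, both tracings in Step 1 are flagged (assuming the values are new since baseline): the fast one through QTcB and the slow one through QT. A composite would collect rate artefacts from both ends.

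**The case against.** The other side has several sound points, and they limit the finding.

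- **QTcF is named.** A reader might infer that the SAP relies on Bazett alone. It does not: the notable-value list includes QTcF. Bazett is the only correction in the grade and change summaries, and what is missing for QTcF is its source.
- **Bazett is prespecified.** The protocol uses it for eligibility, requires it from the ECG machine and names it for analysis. Reporting QTcB is therefore correct, and adding QTcF is a supplement. This does not justify grading uncorrected QT.
- **Table 8 does not supply the bands.** It has one threshold, QTc ≥501 ms, with no 450 or 480 ms limit and no change bands. It shows that the protocol thinks in corrected QT, and no more.
- **The QTcB change summary is not affected by uncorrected QT.** Changes in uncorrected QT are tabulated only through the notable-value list.
- **Heart-rate effects can be partly traced.** RR categories, interval summaries, a listing of all ECG values and pulse flags in SAP 2.8.4.2 are planned. A reader might infer that the trial cannot separate a drug effect on repolarisation from a rate effect. That is too strong: QTcF can be computed from the recorded data, and the 390 ms tracing is still caught by QTcB. In addition, abnormalities the investigator judges clinically significant are recorded as adverse events under protocol 7.3.3.
- **Fever is not shown to drive the result.** Pyrexia was 51% and 53% on the combination in the two phase III studies the protocol describes, and a reader might infer widespread false QTcB flags. Those are proportions with any fever, not proportions febrile at an ECG. The documents state no link to heart rate, and tracings are taken after at least five minutes' rest.

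What remains is that uncorrected QT is placed on the same scale as QTcB without a stated reason, and that a named measure has no definition.

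**Conclusion.** The point holds as a modest, inexpensive improvement to the safety tables. As written, the SAP yields grades for uncorrected QT that depend on heart rate and can contradict the QTcB grade of the same tracing by up to three grades (390 ms at 100 bpm). It also plans a QTcF tabulation that cannot be programmed without a guess.

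Step 1 rests only on the protocol's formula and the SAP's bands. Steps 2 and 3 also assume that constant QTcF represents unchanged repolarisation, so they illustrate the rate dependence of QT and QTcB and do not validate QTcF. No on-study heart rates are given, so the number of misclassified subjects is unknown. The tables are descriptive, in a single-arm study of about 65 subjects. The objective response rate, its confidence interval and the protocol's clinical QTc criteria are not affected.

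**What to change.** In SAP 2.8.4.1:

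1. Remove uncorrected QT from the grade-increase and notable-value categories. Keep it in the interval summaries and listings.
2. Define QTcF = QT/RR^(1/3), with QT in ms and RR in seconds, derived from the recorded QT and RR. The SAP's RR categories are in ms, so state the division by 1000.
3. Show QTcF beside QTcB, each on its own rows, in the grade, change and notable-value tables. Replace the ambiguous list of three measures with these two, tabulated separately.
4. Record QTcF in SAP section 4 as an addition to the protocol's QTcB analysis.

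The cost is one derived variable, a few extra table rows and some SAP wording. No new data are needed, and the protocol-specified QTcB analysis stays as it is.

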2.8.4.2 Vital signs

Vital sign assessments are performed in order to characterize basic body function. The following parameters were collected: height (cm), weight (kg), body temperature ($^{\circ}$ C), heart rate (beats per minute), systolic and diastolic blood pressure (mmHg).

Data handling

Vital signs collected on treatment will be summarized. Values measured outside of on treatment period will be flagged in the listings.

Data analysis

For analysis of vital signs the clinically notable vital sign criteria are provided in [Table 2-5](#) below.

Table 2-5 Clinically notable changes in vital signs

Vital sign (unit)	Clinically notable criteria	
	above normal value	below normal value
Weight (kg)	increase > 10% from Baseline	decrease > 10% from Baseline
Systolic blood pressure (mmHg)	>=180 with increase from baseline of >=20	<=90 with decrease from baseline of >=20
Diastolic blood pressure (mmHg)	>=105 with increase from baseline of >=15	<=50 with decrease from baseline of >=15
Pulse rate (bpm)	>=100 with increase from baseline of >25%	<=50 with decrease from baseline of > 25%
Body temperature	>= 39.1	

The number and percentage of subjects with notable vital sign values (high/low) will be presented.

A listing of all vital sign assessments will be produced and notable values will be flagged. A separate listing of only the subjects with notable vital sign values may also be produced. In the listing, the assessments collected outside of on-treatment period will be flagged.

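### The two RR criteria in the SAP's notable-ECG rule (below 600 ms, and 600 ms or more) cover every value, so the RR part of the rule marks every subject with an RR reading as notable

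*SAP*

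**What the plan says.** Under its data-analysis paragraph, SAP 2.8.4.1 (ECG and cardiac imaging data) states: "The number and percentage of subjects with notable ECG values will be presented". A bulleted set of criteria follows.

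- For QT, QTcF or QTcB there are five lines. Three require a new value in a stated range, and two require an increase from baseline of a stated size.
- For RR there are two lines: below 600 ms, and 600 ms or more. Neither has a new-value or baseline condition.

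The section then commits to a flag: "A listing of all ECG assessments will be produced and notable values will be flagged". It allows, but does not require, a further listing restricted to subjects who have a notable value. RR is expected for everyone: "12-lead ECGs including QT, QTcB, and RR intervals will be obtained local for each subject during the study".

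SAP 2.8.4.2 (Vital signs) has its own notable criteria in Table 2-5. Pulse rate is notable when high (100 bpm or more, with a rise of more than 25% from baseline) or when low ("<=50 with decrease from baseline of > 25" per cent). The output is split by direction: "The number and percentage of subjects with notable vital sign values (high/low) will be presented".

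**The concern.** A notable-value rule is useful only if some values fall outside it. The two RR lines leave nothing outside. An RR value that is ordinary and unchanged since baseline satisfies one of them, so the RR flag is switched on for every record that has an RR value.

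The 12-lead ECG is a named safety measure in the objectives tables of both documents, and this table and flag are how the SAP directs the reader of the report to ECG values of interest. If programmed literally, the RR flag directs the reader nowhere. The optional listing of notable subjects would exclude nobody who has an RR value. The line for 600 ms or more also labels normal rates as notable and puts them in one row with slow ones.

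**Working it through.** There is no power, alpha or sample-size figure behind this point and no stated figure to reproduce. The check is one of logic plus one unit conversion.

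**Inputs.** The RR cut-off of 600 ms, used twice, comes from SAP 2.8.4.1. The conversion comes from protocol Appendix 3, where RR in seconds is "often derived from the heart rate (HR) as 60/HR". The pulse limits of 100 and 50 bpm come from SAP Table 2-5.

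**Step 1: coverage.** For any recorded RR, either RR < 600 or RR ≥ 600 is true, and never both. Testing every whole millisecond from 200 to 3000 confirms it: all values meet exactly one criterion, and none meets neither. So the share of non-missing RR values that are notable is 100% by construction. At subject level, everyone with at least one RR value meets at least one criterion, and a subject with values on both sides of 600 ms meets both. If all of the approximately 65 enrolled subjects have an RR value, that is 65 of 65.

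**Step 2: what each row holds.** HR (bpm) = 60000 / RR (ms), so 60000 / 600 = 100 bpm. The first row is HR above 100. The second row is HR of 100 or lower:

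| HR (bpm) | RR (ms) | Row |
|---|---|---|
| 120 | 500 | below 600 |
| 100 | 600 | 600 or more |
| 80 | 750 | 600 or more |
| 60 | 1000 | 600 or more |
| 50 | 1200 | 600 or more |
| 40 | 1500 | 600 or more |

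Rates of 80 and 40 bpm cannot be told apart by the rule.

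**Step 3: comparison with the SAP's own pulse criteria.** 60000 / 100 = 600 ms and 60000 / 50 = 1200 ms. The lower RR cut-off agrees with the upper pulse limit, except at exactly 100 bpm, which Table 2-5 includes and RR < 600 does not. Nothing in the RR rule corresponds to the lower pulse limit, and nothing corresponds to the change-from-baseline condition in either pulse cell.

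**Illustration only.** The documents give no heart-rate distribution. Assuming normally distributed readings with mean/SD of 65/10, 75/12 or 85/15 bpm, the proportion of readings in the row for 600 ms or more is 1.000, 0.981 or 0.841. Of the readings in that row, 0.067, 0.019 or 0.012 are at 50 bpm or below. Under these assumptions, slow rates would be a small part of a row made up mostly of ordinary ones. The result in Step 1 does not depend on these assumptions.

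**The case against.** The strongest reply is that this is a one-line drafting slip in a descriptive table of a close-out SAP, and that other outputs cover the ground. Much of that stands.

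- A reader might infer that slow heart rate cannot be identified in this study at all. The documents do not support that. Table 2-5 defines a notable low pulse, tabulates it and flags it. SAP 2.8.4.1 also lists ECG values and abnormal findings, tabulates normal and abnormal findings by visit, and says: "In addition, ECG interval values will be also be summarized". Protocol 7.3.3 makes clinically significant ECG abnormalities reportable as adverse events, and 7.3.4 requires event-specific data collection for arrhythmias.
- A reader might also infer that subjects with notable QT values are lost among the rest. They are not. QT has its own five criteria, and SAP 2.8.4.1 separately provides QT/QTcB grade-increase summaries and QTcB change categories. Only the restricted listing would fail to separate them, and that listing is optional.
- The two lines could be a plain split at 600 ms, presented row by row. On that reading the row below 600 ms still isolates rates above 100 bpm. The SAP does not define an overall any-notable count.
- Neither document states an upper RR limit. That 1200 ms was meant is an inference from Table 2-5.

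What the reply does not remove is the rule itself. Both lines sit under the notable heading and feed the flag, so a plain split is in the wrong place. Table 2-5 is not a full substitute. A pulse falling from 62 to 48 bpm is a drop of 14/62 = 22.6%, which misses its 25% condition. The schedule in protocol Table 20 also has an ECG on Day 15 but no vital signs that day. Listings allow a manual search but do not make the pre-specified flag work.

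**Conclusion.** The point holds, with a narrow effect. The RR criteria are exhaustive and have no new-value or baseline condition, so 100% of subjects with a non-missing RR value meet an RR notable criterion and every such record is flagged. The RR rule by itself cannot separate slow from normal rates. This follows from the text and needs no assumption about the data. Only the figure of 65 of 65 assumes that every enrolled subject has an RR value.

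The effect stops at one descriptive safety table, its listing flag and one optional listing. The row below 600 ms, read alone, remains interpretable. ORR, PFS, OS, duration of response, the QT and QTcB summaries, LVEF, adverse events and the pulse criteria are unaffected. A duplicated cut-off is the likely cause, but the intended second limit is not in the documents. It should be corrected because the rule gives a wrong result as written and the correction is nearly free, not because any conclusion of the trial depends on it.

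**What to change.** In SAP 2.8.4.1:

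1. Remove the RR line for 600 ms or more from the notable set. If a simple split of RR at 600 ms is wanted for description, show it outside the notable table and without a flag.
2. Apply the RR criteria only to new on-treatment values, in the same sense as the new-value QT lines.
3. If a slow-rate criterion was intended, replace the removed line with one reconciled with Table 2-5, whose limits of 100 and 50 bpm correspond to RR 600 and 1200 ms. The sponsor should confirm the intended limit, whether a change-from-baseline condition applies as it does for pulse, and how a value exactly at the limit is treated.

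Steps 1 and 2 restore a working flag without a new threshold, but they leave the RR rule with no slow-rate criterion. Low rates would then rest on Table 2-5 and the listings. The cost is two lines of SAP text and one programming condition, with no new data.
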